## **8.2 Dose Level Review Team (DLRT)**

Dose Level Review Meetings (DLRMs) will be held to review data, monitor safety, and make decisions on dose escalation / change decisions. The DLRT will be composed of the investigators or designees, and the following Amgen representatives: medical monitor, early development leader, global safety officer or designee, clinical study manager, biostatistician and clinical pharmacologist. Additional members may be added as needed. The following members are responsible for DLRT decisions: investigators, Amgen medical monitor, and global safety officer or designee. Study decisions by DLRM participants must be unanimous. All available study data, including data collected after the initial DLT window, and including demographics, IP administration, medical history, concomitant medications, adverse events, ECGs, vital signs, laboratory data, efficacy and PK/PD information will be reviewed. In addition to DLTs, all  $\geq$  grade 3 toxicities not meeting DLT criteria will be reviewed and may be considered in DLRT decisions.

A DLRM Charter will not be used.

## **9. Data Screening and Acceptance**

### **9.1 General Principles**

The objective of the data screening is to assess the quantity, quality and statistical characteristics of the data relative to the requirements of the planned analyses.

### **9.2 Data Handling and Electronic Transfer of Data**

Amgen's Clinical Data Management department will provide all data to be used in the planned analyses. The database will be subject to edit checks outlined in the Clinical Data Management Plan (DMP). See details of this section in the DMP.

### 9.3 Handling of Missing and Incomplete Data

#### Imputation Rules for Partial or Missing Start Dates

	Missing	Imputation	Exception
Start date (AE, concomitant medication)	Day	01	Default to Study Day 1 if an adverse event starts the same year and month as Study Day 1 and the flag indicates that the adverse event started on or after the first dose on the Adverse Events eCRF
	Day/Month	01JAN	Default to Study Day 1 if an event started the same year as Study Day 1 and the flag indicates that the adverse event started on or after the first dose on the Adverse Events eCRF
	Day/Month/Year	No imputation	

#### Imputation Rules for Partial or Missing Stop Dates

If the month and year are present, impute the last day of the month. If only the year is present, impute December 31 of that year. If the stop date is entirely missing, assume the event or medication is ongoing. If a partial or complete stop date is present and the 'ongoing' or 'continuing' box is checked, then it will be assumed that the AE or conmed stopped and the stop date will be imputed, if partial. Ensure the imputed stop date is on or after the complete or imputed start date.

### 9.4 Detection of Bias

Lack of protocol compliance and the potential for biased statistical analyses will be examined by assessing the incidence of important protocol deviations (IPD). The clinical study team will identify and document the criteria for IPD.

### 9.5 Outliers

Outlier data will not be excluded unless scientifically justified.

PK serum concentration data will be evaluated for outliers by visual inspection and decisions to re-assay individual samples will be made in accordance with standard pharmacokinetic evaluation practices.

### 9.6 Distributional Characteristics

Where appropriate, the assumptions underlying the proposed statistical methodologies will be assessed. If required data transformations or alternative non-parametric methods of analyses will be utilized.

## **9.7 Validation of Statistical Analyses**

Programs will be developed and maintained, and output will be verified in accordance with current risk-based quality control procedures. Tables, figures and listings will be produced with validated standard macro programs where standard macros can produce the specified outputs.

The production environment for statistical analyses consists of Amgen-supported versions of statistical analysis software, for example the SAS System version 9.4 or later.

Additional statistical software may be used to perform exploratory/ad-hoc analyses.

## **10. Statistical Methods of Analysis**

### **10.1 General Principles**

Descriptive statistics will be provided for selected demographic, safety, PK, PD and biomarker data by dose, dose schedule, and time as appropriate. Descriptive statistics on continuous data will include means, medians, standard deviations (and standard errors for post-baseline data), quartiles, and ranges, while categorical data will be summarized using frequency counts and percentages. Graphical summaries of the data may also be presented. Analysis of data in Part 2 will be done separately for each group (Group 1, 2, 3, 4a, 4b).

When data are summarized by time, the values recorded against the scheduled time points listed in the protocol will be used. When assessing minimum/maximum increases or decreases over the study, all assessments, including unscheduled assessments will be used. Data listings will include all available data from all enrolled subjects unless specified otherwise.

### **10.2 Subject Accountability**

The number and percent of subjects who were enrolled, received investigational product, completed investigational product, discontinued from investigational product (including reasons for discontinuing), completed study, and discontinued the study (including reasons for discontinuing) will be summarized by dose group, by cohort.

Key study dates for the first subject enrolled, last subject enrolled, and last subject's end of study will be presented.

A list of subjects who withdraw early will be reviewed. It will include the reason and timing of the withdrawal. Similarly, the reason any subject is excluded from an analysis set will also be reviewed.

### 10.3 Important Protocol Deviations

IPD categories are defined by the study team before the first patient visit and updated during the IPD reviews throughout the study prior to database lock. These definitions of IPD categories, sub-category codes and descriptions will be used during the course of the study.

The final IPD list is used to produce the Summary of IPDs table and the list of Subjects with IPDs. In addition, a separate listing of all inclusion and exclusion deviations will be provided.

### 10.4 Demographic and Baseline Characteristics

Demographic (ie, age, sex, race, ethnicity, and baseline characteristics (height, weight, ECOG status, disease stage criteria, and BMI) will be summarized by dose using descriptive statistics. If multiple races have been reported for a subject, the subject will be categorized as multiple race as well as by the combination of races.

A listing of the demographic and baseline characteristics will be provided. In addition listings of medical history, surgical history, prior anti-cancer usage and prior radiotherapy usage will be provided.

### 10.5 Safety Analyses

#### 10.5.1 Adverse Events

The Medical Dictionary for Regulatory Activities (MedDRA) version 20.1 or later will be used to code all adverse events to a system organ class and a preferred term. The subject incidence of adverse events will be summarized for all treatment-emergent, serious treatment emergent, treatment-related to AMG 820 or pembrolizumab, those leading to withdrawal of IP, fatal and of special interest. **Immune-mediated events associated with oncologic immunotherapies AMQ can be considered as event of interest and list of EOI's will be provided programming note of TFL shell document.** The severity of each adverse event will be graded using CTCAE version 4.0 criteria.

Subject incidence of all treatment-emergent, serious treatment-emergent, treatment-related to AMG 820 or pembrolizumab, those leading to withdrawal of IP, and fatal AE will be tabulated by system organ class and preferred term, where treatment refers to IP. Where appropriate the tables will also be presented by worst grade. The above adverse event tables will not be created if two or fewer subjects experience the adverse event.

Details of each adverse event from will be listed. Listings and/or narratives of any on-study deaths, serious and significant treatment-emergent adverse events, including early withdrawals due to adverse events, also will be provided should they occur.

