7.2.4 Long-term Follow-up

After the safety follow-up visit all subjects will enter the long-term follow-up. Subjects will be contacted by clinic visit or telephone to assess survival, disease status and initiation of first subsequent anti-tumor therapy following end of AMG 820 and pembrolizumab treatment.

Contact for all subjects will be attempted every 12 weeks (\pm 28 days) following the safety follow-up visit, as applicable, until death, subject withdraws full consent, or up to 12 months after subject's enrollment for the study, whichever comes first.

For subjects who discontinued treatment for any reason other than confirmed PD, every effort should be made to perform radiographic imaging (CT or MRI) of the chest, abdomen and pelvis, along with tumor assessments of all other sites of disease every 12 weeks until documentation of confirmed PD per irRECIST, clinical progression, start of new anticancer therapy, or up to 12 months after subject's enrollment for the study, whichever occurs first.

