9.2.2 Adverse Events

9.2.2.1 Reporting Procedures for Adverse Events That do not Meet Serious Criteria

The investigator is responsible for ensuring that all adverse events observed by the investigator or reported by the subject that occur after first dose of AMG 820 or pembrolizumab through the safety follow-up visit (ie, 135 [+7] days after the last dose of AMG 820 or pembrolizumab, whichever is later) are reported using the Event CRF.

The investigator must assign the following adverse event attributes:

- Adverse event diagnosis or syndrome(s), if known (if not known, signs or symptoms),
- Dates of onset and resolution (if resolved or improved to a lower grade),
- Severity [and/or toxicity per protocol],
- Assessment of relatedness to AMG 820 and/or pembrolizumab and
- Action taken.

The adverse event grading scale used will be the CTCAE version 4.0. The grading scale used in this study is described in [Appendix A](#). The investigator must assess whether the adverse event is possibly related to the AMG 820 and/or pembrolizumab. This relationship is indicated by a “yes” or “no” response to the question: Is there a reasonable possibility that the event may have been caused by the investigational product(s)?

The investigator must assess whether the adverse event is possibly related to any study-mandated activity (eg, administration of investigational product, protocol-required procedure (including any screening procedure(s))). This relationship is indicated by a “yes” or “no” response to the question: “Is there a reasonable possibility that the event may have been caused by a study activity (eg, administration of investigational product, protocol-required procedure)?”

The investigator is responsible for reviewing laboratory test results and determining whether an abnormal value in an individual study subject represents a clinically significant change from the subject’s baseline values. In general, abnormal laboratory findings without clinical significance (based on the investigator’s judgment) are not to be recorded as adverse events. However, laboratory value changes that require treatment or adjustment in current therapy are considered adverse events. Where applicable, clinical sequelae (not the laboratory abnormality) are to be recorded as the adverse event.

If the severity of an adverse event changes from the date of onset to the date of resolution, record a single event for each level of severity on the Event CRF.

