10.4.4.1 Adverse Events

Subject incidence of all treatment-emergent adverse events will be tabulated by system organ class and preferred term. The number and percentage of subjects reporting adverse events will be evaluated overall and by AMG 820 dose level and will also be tabulated by relationship to AMG 820. Tables of dose limiting toxicities, fatal adverse events, serious adverse events, adverse events leading to withdrawal from investigational product or other protocol-required therapies, and significant treatment-emergent adverse events will also be provided.

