#### 4. Study Endpoints and Covariates

##### 4.1 Study Endpoints

###### Primary Endpoints:

- Dose limiting toxicities (DLT), treatment-emergent adverse events, treatment-related adverse events and clinically significant changes in vital signs, physical examinations, and clinical laboratory tests
- Objective response rate (ORR) per irRECIST in subjects treated at the recommended combination dose

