### Treatment-Emergent Adverse Event( TEAE)

A treatment-emergent adverse event is any adverse event starting on or after the first dose of AMG 820 **or pembrolizumab**, as determined by the flag indicating if the adverse event started prior to the first dose on the Adverse Events Summary CRF, and up to and including **135 [+7]** days after **the last dose of AMG 820 or pembrolizumab, whichever is later.**

---

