### Treatment-Related Adverse Event

Treatment-related AEs are adverse events deemed by the investigator to be possibly or probably related to AMG 820 or pembrolizumab. The investigator must assess whether the adverse event is possibly related to any study-mandated activity (eg, administration of investigational product, protocol-required procedure (including any screening procedure(s))). This relationship is indicated by a “yes” or “no” response to the question: “Is there a reasonable possibility that the event may have been caused by a study activity.” If the severity of an adverse event changes from the date of onset to the date of resolution, record a single event for each level of severity on the Event CRF.

The Investigator is expected to follow reported adverse events until stabilization or reversibility.

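### SAP 10.5.1 drops adverse-event incidence tables, including serious and fatal events, when two or fewer subjects are affected; the protocol sets no such minimum and the SAP does not declare the change

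*SAP*

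**What the plan says.** The primary endpoints in SAP 4.1 begin with "Dose limiting toxicities (DLT), treatment-emergent adverse events, treatment-related adverse events", so adverse-event incidence is part of a primary endpoint.

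SAP 10.5.1 has two layers. Its first paragraph says subject incidence will be summarised for each category of event. Its second paragraph describes the detailed tables, covering all treatment-emergent, serious treatment-emergent and treatment-related events, and "those leading to withdrawal of IP, and fatal AE will be tabulated by system organ class and preferred term, where treatment refers to IP". That paragraph ends with the threshold: "The above adverse event tables will not be created if two or fewer subjects experience the adverse event". The section then provides for listing every adverse event, and for listings and/or narratives of deaths, serious events and withdrawals. DLTs are handled in SAP 10.5.1.1, where a summary is given if any occur.

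Protocol 10.4.4.1 tabulates all treatment-emergent events by system organ class and preferred term. It also promises "Tables of dose limiting toxicities, fatal adverse events, serious adverse events, adverse events leading to withdrawal from investigational product" and significant treatment-emergent events. It states no minimum count. SAP 10.10, the section for departures from the protocol, lists only the removal of RECIST 1.1.

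**The concern.** A rule in the SAP changes how part of a primary endpoint is reported, the protocol has no counterpart to it, and the section meant to record such changes is silent. The tables affected include those for serious and fatal events, where low counts are expected and still matter.

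The sentence also cannot be programmed without further decisions. *The adverse event* could mean a category, so that the whole fatal table disappears when two subjects have fatal events. It could also mean a single preferred term, so that individual rows disappear. Nor does the sentence say whether subjects are counted within a Part 2 group, within a dose level or over the whole study. SAP 10.1 says Part 2 data are analysed separately by group, while Protocol 10.4.4.1 evaluates adverse events overall and by AMG 820 dose level. Two programmers following the text could produce different reports.

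**Working it through.** **The plan's own safety figure.** Protocol 10.2 and SAP 3.2 give a 47–91% probability of at least one DLT among 6 subjects for true rates of 10–33%. With 1 − (1 − p)^6: p = 0.10 gives 1 − 0.531 = 0.469, and p = 0.33 gives 1 − 0.090 = 0.910. The figure is reproduced. It concerns DLTs and is not affected by the threshold.

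**Inputs.** The threshold is 2 subjects (SAP 10.5.1). Stage 1 group sizes are 18, 10, 19, 10 and 10, total 67 (SAP 8.1). Full group sizes are 43, 29, 55, 29 and 29, and overall enrolment is 67 to 197 (SAP 3.2). The 5% and 10% true rates are illustrative assumptions, not figures from the documents.

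**Formulas.**
- Largest untabulated incidence: 2/n.
- Exact (Clopper-Pearson) two-sided 95% upper limit for 2/n: the 0.975 quantile of Beta(3, n − 2).
- Probability of no table: P(X ≤ 2) = (1 − p)^n + n·p·(1 − p)^(n−1) + [n(n − 1)/2]·p²·(1 − p)^(n−2).

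**Worked cases at p = 0.10.**
- n = 10: 0.3487 + 0.3874 + 0.1937 = 0.930.
- n = 18: 0.1501 + 0.3002 + 0.2835 = 0.734.

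| Subjects counted | n | 2/n | 95% upper limit | P(no table), true 10% | P(no table), true 5% |
|---|---|---|---|---|---|
| Stage 1, Groups 2, 4a, 4b | 10 | 20.0% | 55.6% | 93.0% | 98.8% |
| Stage 1, Group 1 | 18 | 11.1% | 34.7% | 73.4% | 94.2% |
| Stage 1, Group 3 | 19 | 10.5% | 33.1% | 70.5% | 93.3% |
| Full Groups 2, 4a, 4b | 29 | 6.9% | 22.8% | 43.5% | 82.5% |
| Full Group 1 | 43 | 4.7% | 15.8% | 18.2% | 63.5% |
| Full Group 3 | 55 | 3.6% | 12.5% | 7.7% | 47.7% |
| Pooled, smallest study | 67 | 3.0% | 10.4% | 3.1% | 34.3% |
| Pooled, largest study | 197 | 1.0% | 3.6% | 0.0% | 0.3% |

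The level of counting therefore decides whether the rule matters much. By group in stage 1 it would usually remove an event with a true 10% rate; pooled it rarely would.

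**Source of relatedness.** The SAP 6 definition opens by tying treatment-related events to AMG 820 or pembrolizumab, and SAP 10.5.1 does the same. The only CRF question it then quotes is "Is there a reasonable possibility that the event may have been caused by a study activity", which by its own text covers protocol-required and screening procedures. Protocol 9.2.2.1 has a separate yes/no question on the investigational product, and the sample form in Protocol Appendix B keeps product relationship apart from a study-procedure box. The definition is right, but the field it derives from is not named.

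**Window.** SAP 6 runs the treatment-emergent window to 135 (+7) days after the last dose, with no cut at new therapy. Protocol 9.2.2.1 collects adverse events over the same window, so the two agree.

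**The case against.** The best defence is that nothing disappears from the report. Every adverse event is listed, and deaths, serious events and withdrawals have listings and/or narratives. DLTs are summarised with no threshold, and the first paragraph of SAP 10.5.1 still promises incidence by category. With two affected subjects, a reader can count them and divide by the group size. The final table list also sits in a separate system (SAP 11) that is not available here. Most of this stands, and it limits the finding to lost tabulation. It does not remove the finding. A listing carries no denominator or percentage, the protocol promises tables, and the SAP does not say that the category summaries are exempt from a sentence that refers to the tables above.

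The by-group probabilities are also the unfavourable end of the range. That is fair, and the pooled figures are shown beside them, but the SAP does not say that counts are pooled.

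Four stronger readings are tempting, and the documents do not support them:
- A reader might infer that the rule conceals rare severe events or misreports the endpoint. The listings, narratives and summaries rule that out.
- A reader might set 2 of 6 subjects (33%) against the Part 1 intolerance figure. That figure is a DLT rate, and DLTs fall outside the rule.
- A reader might infer that biopsy or other procedure events will be counted as drug-related. The operative sentence of the SAP 6 definition and SAP 10.5.1 both say related to the two drugs.
- A reader might call the missing cut at new anticancer therapy an error. The window matches protocol collection. The Events of Clinical Interest window (Protocol 6.2.4.9 and 9.4) is no precedent for a cut. It ends 135 (+7) days after the last dose or after the start of new therapy, and in 6.2.4.9 the earlier applies. When new therapy follows the last dose, the last-dose limit is the earlier one.

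**Conclusion.** The threshold is an undeclared departure from Protocol 10.4.4.1 that affects reporting of part of a primary endpoint, and its unit and level are undefined. Counted by group, it could leave an event seen in 20% of a 10-subject stage out of the tables. At an assumed true rate of 10%, it would remove the table with probability 93% (n=10) or 73% (n=18). Pooled at n=67 the probability is 3%. These sizes rest on the assumed rate and on the level of counting, which the SAP leaves open. The loss is tabulated incidence by system organ class and preferred term, not the events themselves. No sample size, power or alpha figure changes.

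The relatedness point is a wording clean-up. A summary truncated at new therapy would be an optional improvement, not the correction of an error.

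**What to change.** 1. In SAP 10.5.1, delete the two-or-fewer threshold. Alternatively, limit it to non-serious, non-fatal preferred-term sub-tables, state the unit and level of counting, and declare it in SAP 10.10.
2. In SAP 6, name the investigational-product causality item of Protocol 9.2.2.1 (yes for AMG 820 and/or pembrolizumab) as the source of the treatment-related flag.
3. Optionally, add a treatment-emergent summary truncated at the start of the first subsequent anticancer therapy, beside the full 135-day table. Protocol 7.2.4 already collects "initiation of first subsequent anti-tumor therapy", and Protocol 6.5 records start dates of concomitant therapies through 135 (+7) days.

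Items 1 and 2 cost SAP wording and a few short tables. Item 3 costs one extra table. None needs new data.

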#### **10.5.1.1 Dose Limiting Toxicities**

Summary of the subject incidence of dose limiting toxicities (DLT) will be provided should they occur.

#### **10.5.2 Laboratory Test Results**

##### **10.5.2.1 Chemistry, Hematology and Coagulation**

Clinical chemistry, hematology, and urinalysis data will be listed and reviewed for each subject. Values outside the normal laboratory reference ranges will be flagged as high or low on the listings. Depending on the size and scope of changes in laboratory data, summaries of laboratory data over time and/or changes from baseline over time may be provided. Tables of maximum shifts from baseline for selected laboratory values may also be provided. The worst value for each subject within the time interval of interest will be used for subjects with multiple measurements within the interval. Subjects with missing data for a defined time interval will not contribute to the tabulations for that time interval.

**Corrected calcium will also be included in above mentioned analysis, which will be calculated as below**

**Corrected Calcium =  $[0.8 * (\text{normal albumin} - \text{subject albumin(g/dl)})] + \text{serum calcium(mg/dl)}$**

**Where Normal Albumin level will be considered as 4 g/dl.**

Subject incidence of liver function test results (including AST, ALT, Total Bilirubin (TBL), and Alkaline Phosphatase (ALP)) will also be summarized by dose group. In addition, subject incidence of suspected Hy's Law cases will also be presented by dose group.

